2. OBJECTIVE(S) AND ENDPOINT(S)

[figure not shown]
Objectives	Endpoints
Primary	
To assess the safety and tolerability of single IV doses of GSK2831781 in healthy	• Laboratory safety data (haematology, clinical chemistry, urinalysis)
volunteers and psoriasis patients.	• Vital signs (blood pressure, heart rate, body temperature)
	• 12-lead ECGs
	• Adverse events
	Inflammatory cytokine levels
Secondary	
To evaluate the pharmacology and clinical effect of a single IV dose of GSK2831781 in a DTH model in healthy volunteers.	• Change from baseline (PPD 1st challenge) of induration diameter from re-challenge at 3 days post-dose
	• Duration of induration in the re- challenge
	• Change from baseline (PPD 1st challenge) of LAG-3+ cells in biopsies of re-challenged skin at 3 days post- dose, measured by IHC
To evaluate the pharmacology of a single IV dose of GSK2831781 in psoriasis patients.	• Change from baseline in LAG-3+ cells in lesional biopsies at Day 29 measured by IHC
To evaluate the pharmacokinetics of single IV doses of GSK2831781 in healthy volunteers and psoriasis patients.	 GSK2831781 PK parameters following single intravenous dose: AUC(0-∞), AUC(0-t), AUC(0- Week4), %AUCex, Cmax, tmax, tlast, CL, Vss, MRT, λz and t ½ when assessable
To evaluate the immunogenicity of GSK2831781 administered as a single IV dose in healthy volunteers and psoriasis patients.	• Antibodies to GSK2831781 in serum
To evaluate the effect of a single IV dose of GSK2831781 on disease activity in psoriasis patients.	• Change from baseline and actual PASI scores at Day 15, 29, 43, 85, 121 and follow up
	 Proportion of subjects who achieve ≥50% and ≥75% improvement from baseline in PASI score at Day 15, 29,

Objectives	Endpoints	
	43, 85,121 and follow up (PASI 50 and PASI 75)	
	• Change from baseline and actual PLSS scores at Day 15, 29, 43, 85, 121 and follow up	
	• Change from baseline and actual PGA scores at Day 15, 29, 43, 85 and 121	
	• Proportion of subjects in each PGA score category at Day 15, 29, 43, 85 and 121	
	• Proportion of subjects achieving PGA 0/1 and at least a 2 point improvement at Day 15, 29, 43, 85 and 121	
Exploratory		
To evaluate the effect of a single IV dose of GSK2831781 in psoriasis patients on biomarkers.	• Histopathological scoring of psoriatic lesional biopsies in patients with psoriasis - Ki67, CD3 and epidermal thickness	
	• Transcriptomic analysis of psoriatic lesional biopsies in patients with psoriasis	

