4.3.3. Activity

Part A and B: Subjects will abstain from strenuous exercise for 48 hours prior to dosing and prior to each blood collection for clinical laboratory tests. Subjects may participate in light recreational activities during studies (e.g., watch television, read).

Part B: Subjects must not sunbathe or use a tanning device (e.g. sunbed or solarium) whilst taking the study medication and until Day 43. Subjects will be advised that when they are outdoors they should wear protective clothing (e.g. sun hat, long sleeves) and use a broad spectrum UVA/UVB sunscreen and lip balm (SPF \geq 30) when outdoors.

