5.14.2.3. Part B

Use of the following prescription and non-prescription drugs are not permitted for the following periods a detailed below:

Restricted Medication	Restricted Time Period	Details
Low potency local corticosteroid "rescue" treatment for psoriasis flares may be used, but not at or near the index plaque being used to	7 days prior to Day - 1 to Day 43	As a rescue medication only upon discussion with investigator.
assess efficacy or the biopsy plaque. Worsening of the psoriasis may, if needed, be managed by introducing topical steroid therapy (if not already in use) or increasing the strength of topical steroid being used or using a higher potency steroid.		Example medications: Weak topical steroids (class VI or VII only) for use limited to the face, axillae, or genitalia as required except on the lesions of interest. Alclometasone dipropionate 0.05% cream and 0.05% ointment Desonide 0.05% cream, 0.05% foam, 0.05% gel and 0.05% lotion Fluocinolone acetonide 0.01% shampoo and 0.01% solution Flurandrenolide 0.025% cream Triamcinolone acetonide 0.025% cream and 0.025% lotion
Over-the-counter non-medicated,	24hr prior to Day -1	Not allowed within 24hrs
topical emollients/moisturizers Topical Vitamin D analogues High dose topical corticosteroids Topical coal tar	to Day 43 7 days prior to Day - 1 to Day 43	before assessment visit Always
Single-treatment phototherapy (ultraviolet B or self-treatment with tanning beds).	14 days prior to Day- 1 to Day 43	Always
Anti-TNF/IL12/23 or other monoclonal antibodies.	12 weeks prior to Day -1 to Follow up ¹	Always

Restricted Medication	Restricted Time Period	Details
Systemic therapies including oral steroids, Fumaric acid esters, Oral retinoids Acitretin, Oral steroid.	5 half lives prior to Day -1 to Follow-up ¹	Always
Methotrexate and Cyclosporine	8 weeks prior to Day -1 to Follow-up ¹	
PUVA with psoralen	4 weeks prior to Day -1 to Follow-up ¹	
Narrow therapeutic index medications	Screening to Follow- up ¹	Always

1. Follow-up varies with dose (See Table 1).

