8.3.4.1. Statistical Methodology Specification

Endpoint / Variables

Change from baseline in PASI scores

Model Specification

Same MMRM model as for CFB in induration (Section 8.1.4.1)

Model Checking & Diagnostics

Same approach as in Section 8.1.4.1

Model Results Presentation

 Table/Figure of the LS means of CFB and 95% CI (by treatment and visit), as well as treatment differences and 95%CI

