13. BAYESIAN ANALYSES (PART B)

To aid decision making, the following posterior probabilities, will be evaluated:

For **PASI/PLSS**:

- Difference of interest = Difference (active placebo) in % CFB,
- Probabilities of interest

P(difference < 0) $P(difference \le 10\%)$ $P(difference \le 20\%)$ $P(difference \le 30\%)$ $P(difference \le 40\%)$

For **total LAG3 cells** for the epidermis and dermis:

- Difference of interest = Difference (active placebo) in % CFB
- Probabilities of interest

P(difference < 0) $P(difference \le 30\%)$

For Ki67 and epidermis thickness:

- Difference of interest = Difference (active placebo) in CFB
- Probabilities of interest

P(difference < 0)

The active and placebo treatment groups mentioned above are defined as follows:

- Subjects in the active group are defined as psoriasis patients that received the doses 1.5mg/kg and 5mg/kg (pooled cohorts 8 and 9). In total, 12 subjects are on active.
- Subjects in the placebo group are defined as psoriasis patients that received placebo in cohorts 7-9. In total, 9 subjects are on placebo.

The propobabilities described above may also be calculated for each dose (i.e. 1.5mg/kg versus placebo and 5mg/kg versus placebo).

For PASI and PLSS, the change from baseline to lowest non-missing post-baseline response will be derived for each subject, considering all their available assessments out to day 85. The Bayesian analyses will be conducted for these derived endpoints to provide an overall summary, as oppose to a distinct assessment at each timepoint. For the other endpoints changes from baseline to day 29 will be assessed.

Changes from baseline in each parameter will be analysed using a linear regression, including treatment (active and control as defined above) and baseline score:

 $Y_i \sim \text{Normal}(\mu_i, \text{precision} = \tau)$ $\mu_i = \beta_0 + \beta_1 Base_i + \beta_2 Treatment_i$ Where Y_i is the observed change from baseline response for each subject as defined above.

Non-informative conjugate prior distributions are assigned to the unknown parameters:

- Intercept and slope coefficients: β_0 , β_1 , $\beta_2 \sim \text{Normal}(0, \text{precision} = 10^{-3})$ Sensitivity analysis with precion=0.1
- Between-subject precision (1/variance): $\tau \sim$ Gamma (shape = 0.001, rate = 0.001), i.e. $E(\tau) = 1$

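### The go/no-go PASI and PLSS result is each subject's lowest score out to Day 85, but several psoriasis treatments are barred only to Day 43 and no analysis rule separates the later scores

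*SAP*

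**What the plan says.** **Restrictions.** In the Protocol 5.14.2.3 table, the row for "Topical Vitamin D analogues High dose topical corticosteroids Topical coal tar" runs from 7 days before Day -1 to Day 43. Single-treatment phototherapy is barred "14 days prior to Day- 1 to Day 43". Protocol 4.3.3 lifts the sunbathing and tanning-device restriction on the same day. The row on low-potency local corticosteroid, which also ends at Day 43, says that such "treatment for psoriasis flares may be used, but not at or near the index plaque being used to" assess efficacy, nor on the biopsy plaque. The same table lets worsening be managed by starting or stepping up topical steroid, including to a higher potency. Systemic agents, biologics, methotrexate, cyclosporine and PUVA stay barred to follow-up.

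**Endpoints.** Protocol Section 2 lists "Change from baseline and actual PASI scores at Day 15, 29, 43, 85, 121 and follow up", with the same days for PLSS; PGA stops at Day 121.

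**Analysis.** In SAP Section 13 the change to the lowest PASI and PLSS is "derived for each subject, considering all their available assessments out to day 85". It feeds posterior probabilities meant to aid decisions, for 12 active subjects (Cohorts 8 and 9) and 9 placebo subjects (Cohorts 7 to 9). SAP Appendix 9 places this output, Table 2.13, under go/no-go endpoints. SAP 8.3.2 notes that Day 85 PASI was not assessed in Cohort 7. Protocol Appendix 6 (Amendment 9) records Day 85 efficacy assessments as added after the Cohort 7 review, so I take this to cover PLSS too. The MMRMs in SAP 8.3.4.1 and 8.4.4.1 contain treatment, visit, their interaction and baseline. Concomitant medication is classified by study phase and listed.

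**The concern.** A lowest-score rule lets a single visit stand for the subject. Of the visits that can supply the minimum (Days 15, 29, 43 and 85), Day 85 falls 42 days after the restrictions end. If a subject has used a topical vitamin D analogue, a potent topical steroid or UVB by then, the score reflects that treatment as well as GSK2831781 or placebo. Nothing in SAP 8.3 to 8.5, Section 13 or the missing-data appendix removes, flags or tests the effect of such scores. The one confounding check in the protocol (3.3.1) concerns immunosuppressants and experimental medicines between follow-up and final surveillance, which is a different period and a different set of drugs.

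The 3 Cohort 7 placebo subjects have three chances at a low score, while the other 6 placebo subjects and all 12 active subjects have four. That alone tilts the comparison slightly towards active. With 12 against 9 subjects, a few treated patients can move the reported probabilities. The Day 85 and later MMRM contrasts, PASI 50/75 and PGA responder tables share the first problem but not the minimum.

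**Working it through.** **The plan's own precision figure.** Protocol 9.2.1 gives a 95% CI half-width of ±26% for percentage change in PLSS with n = 6 and SD 24.8%. Check: t(0.975, 5 df) × 24.8/√6 = 26.03. It reproduces, and I use SD 24.8 below.

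**Inputs from the documents.** 12 active subjects with four visits; 6 placebo subjects (Cohorts 8 and 9) with four; 3 placebo subjects (Cohort 7) with three. SAP 13 reports thresholds of 0, 10, 20, 30 and 40 points on the difference in percentage change.

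**Assumptions not in the documents.** Within-subject correlation between visits of 0.5 to 0.8; other treatment lowers the Day 85 value by 40 points of baseline (30 to 50 as a range); the numbers of users.

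**Step 1: unequal visits, no other treatment, no drug effect.** By simulation, the mean minimum over four visits is -18.06 against -14.85 over three (correlation 0.5), or -11.44 against -9.41 (correlation 0.8). Three of nine placebo subjects lack the fourth visit, so the active minus placebo difference is -(18.06 - 14.85) × 3/9 = -1.07, or -(11.44 - 9.41) × 3/9 = -0.68. Negative favours active.

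**Step 2: how far one treated visit moves a subject's minimum.** A 40-point fall at Day 85 partly replaces an earlier low score, so the minimum moves by less than 40: by m = 23.4 (correlation 0.5) or 28.7 (correlation 0.8).

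**Step 3: shift in the group difference** = m × (placebo users/9 - active users/12), positive meaning towards no difference.
- 3 placebo, 1 active: m × (3/9 - 1/12) = m × 0.25 = 5.8 to 7.2 points.
- 1 placebo, 0 active: m/9 = 2.6 to 3.2 points.

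**Step 4: effect on the reported probabilities.** SE = 24.8 × √(1/12 + 1/9) = 10.9. Suppose a true benefit of 20 points and use a normal approximation, ignoring the baseline covariate and the priors. With 3 placebo and 1 active users, P(benefit > 0) falls from 0.97 to Φ((20 - 5.8)/10.9) = 0.90 or Φ((20 - 7.2)/10.9) = 0.88. P(benefit ≥ 10) falls from 0.82 to 0.65 or 0.60.

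**Step 5: equal use.** If a proportion p of subjects with a Day 85 visit use other treatment in both arms, the active mean moves by p·m and the placebo mean by only p·m × 6/9. The excess is p·m/3 in favour of active, on top of Step 1. At p = 0.5 this gives -(0.5 × 23.4/3 + 1.07) = -5.0 to -(0.5 × 28.7/3 + 0.68) = -5.5 points.

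**Step 6: wider range, no drug effect.** Simulation with 30- or 50-point effects and 25% or 50% use gave:

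| Use after Day 43 | Active minus placebo, best score | Chance the observed difference favours active |
|---|---|---|
| Equal, 25% or 50% | -2.2 to -7.1 | 58% to 71% |
| 50% active, 25% placebo | -6.1 to -13.5 | 72% to 85% |
| 25% active, 50% placebo | +0.1 to +2.6 | 42% to 50% |
| Any, minimum taken to Day 43 only | about 0 | not tabulated |

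**The case against.** The strongest reply concerns exposure. SAP 3.1 has PASI and PLSS evaluated when the last Cohort 9 patient completes Day 43, and Appendix 9 assigns the PASI/PLSS Bayesian output to that delivery. Few Cohort 9 subjects may have a Day 85 score by then and Cohort 7 has none, so Day 85 enters mainly through Cohort 8 (6 active, 3 placebo). The 3-placebo scenario would then mean every Cohort 8 placebo patient; even with complete data it is 3 of 6 against 1 of 12. This stands as a reduction. It does not close the gap: Day 85 scores already available still enter, and SAP 14.9.3 leaves open a re-run at final analysis.

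It also stands that the trial has a safety primary objective and no formal hypotheses, that the interim has no planned effect on study conduct, that the MMRM shows Day 43 separately, and that individual plots and medication listings let a reader look for affected subjects.

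Three stronger readings are tempting and not supported.
- That the late contrast is necessarily pulled towards no difference, because untreated patients seek other therapy. The documents give no usage by arm, and under the best-score rule equal use favours active.
- That each user moves the result by the full assumed effect. That would give 40 × 0.25 = 10 points and P(benefit ≥ 10) of 0.50, but it ignores that the endpoint is a minimum.
- That topical steroids are simply barred to Day 43 and unrestricted afterwards. Low-potency rescue away from the study plaques is allowed earlier, and Protocol 5.14.1 leaves other medication to case-by-case consideration. The table also bars high-dose topical steroid throughout the period to Day 43 while allowing a higher-potency steroid for worsening; the sponsor must reconcile these entries.

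**Conclusion.** The point holds. The restriction on several psoriasis treatments ends at Day 43, the go/no-go derivation reaches Day 85, and nothing in the SAP distinguishes scores recorded after such treatment. The direction is unknown. Under the assumed 40-point effect, the best-score difference shifts by about 6 to 7 points with 3 placebo and 1 active users and by about 3 points with a single placebo user. Equal use shifts it by 2.2 to 7.1 points towards active over the ranges tried. Part of that, about 0.7 to 1.1 points, arises with no other treatment at all, because Cohort 7 lacks Day 85. These sizes rest on assumed effects, correlations and usage; the documents supply only the SD, the group sizes and the visit schedule. The matter bears on an internal decision table and on secondary efficacy displays, not on the primary safety objective. It merits correction because the remedy is cheap.

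**What to change.** No clinical rule needs to change for the analysis to be put right.

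1. In SAP 13, derive the lowest PASI and PLSS from Days 15, 29 and 43, which every cohort has. Make this the main run, or at least report it beside the Day 85 version, and fix which one leads before the results are seen. This needs no medication data and equalises the scheduled visits across cohorts.
2. From the concomitant-medication data, flag each subject with a score after first use of a therapy whose restriction ended at Day 43, and show the flag in the PASI, PLSS and PGA plots and tables.
3. Add a sensitivity MMRM for PASI and PLSS and sensitivity responder tables excluding those scores. Keep these as sensitivity analyses: whether such scores should count as missing, as non-response or as observed is a choice of estimand, and patients who start other treatment may differ from those who do not.

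The cost is SAP wording, one derived flag and a few extra outputs. The Day 43 version can miss a late response, and it does not remove any effect of rescue allowed before Day 43. UV or tanning use may be incompletely recorded, so the flag in items 2 and 3 may miss some users.

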14. APPENDICES

14.1. Appendix 1: Protocol Defined Schedule of Events

14.1.1. Healthy volunteers (no DTH)

Protocol Activity	Base- line		In Clinic Period										Out Patient Visits											
					ay 1			Day 2	Day 3	Day 4	Day 8													
	Day -1	Pre- dose	0 hour	2 hour post- infusion start	4 hour post- infusion start			24 hour post- infusion start			168 hour post- infusion start	Day 11	Day 15	Day 18	Day 22	Day 25ª	Day 29 ^k	Day 43	Day 571	Day 85	Day 121			
Window											±1d	±1d	±1d	±1d	±1d	±1d	±1d	±2d	±2d	±2d	±3d			
Admission to the unit	X																							
Discharge from the unit										Х														
Brief physical	Χ																							
Urine Drug and Alcohol Screen	Х																							
Administer IV Dose (2 hour infusion)			∢	> i																				
Safety Assessme	ents					-				-											\neg			
Vital Signs	Χ	X		X	X	X	X	X	Х	X	X		Χ		Χ		X	Χ	Χ	Χ	Χ			
12 - Lead ECG	Χi	Χ	◄	▶□		Х				Х														
Concomitant Medications	◄																							
Adverse Events Assessment / SAE'sc	4																							
Laboratory Asses		s																						
Haematology	X					X	X			X	X	X	X	X	X	X	X	Х	Χ	X	X			
Chemistry	X					Χq	Χα			X	X		X		Х		Χ	Х	Χ	X	X			
Urinalysis	Χ					X	X			X	X		X		X		X	Х	Х	X	X			

Protocol Activity	Base- line		In Clinic Period										Out Patient Visits												
					ay 1			Day 2	Day 3	Day 4	Day 8														
	Day -1	Pre- dose	0 hour	2 hour post- infusion start	4 hour post- infusion start	6 hour post- infusion start	12 hour post- infusion start	post-	post-	72 hour post- infusion start	168 hour post- infusion start	Day 11	Day 15	Day 18	Day 22	Day 25ª	Day 29k	Day 43	Day 571	Day 85	Day 121				
Window											±1d	±1d	±1d	±1d	±1d	±1d	±1d	±2d	±2d	±2d	±3d				
CMV and EBV serology sample	х																								
Viral load sample (CMV, EBV, HSV, VZV) ^e	x																								
PK Samplef						4									•										
Immunogenicity Sample		Х									Х						Х			х					
Immune Cell Phenotypings		Х				Х		Х		Х	Х		Х				Х		Х	х	х				
CD16 and LAG-3 Receptor occupancy		Х				Х		Х		Х	Х		х				х		х	Х	X				
Cytokine Sample		Χ				Х	Х	Х	Х																
G-CSF Sample		Χ				Х		Х		Х	Х		Χ				Х	Х	Х	Х	Х				
sLAG-3 Sample		Χ				X		X		X	X		Х				Х	Х	Χ	Х	Х				
Blood Transcriptomics Sample		X						х																	
Ex Vivo Antigen/Cytokine Stimulation Test		X						Х																	

Protocol Activity	Base- line				In	Out Patient Visits															
					ay 1			Day 2	Day 3	Day 4	Day 8										
	Day -1	Pre- dose	Pre- 0 hour post- post- post- post-					24 hour post- infusion start	post-	post-	nour nost-	Day 11	Day 15	Day 18	Day 22	Day 25ª	Day 29k	Day 43	Day 571	Day 85	Day 121
Window						Ĺ .					±1d	±1d	±1d	±1d	±1d	±1d	±1d	±2d	±2d	±2d	±3d
In vitro LAG-3+ activity		Х		Х							Х										
PGx Sample	Χħ																				\Box

- x oampie X:

 Cohort 0.0003mg/kg last out patient visit will be on Day 25.

 Continuous 2-lead ECG during infusion. Only significant abnormalities during this time will be databased.

 A targeted physical examination may take place if guided by AE reporting relating to Section 6.3.4, Section 6.3.5 and Section 6.3.6..

 Liver Chemistry and CRP only

- Viral load sample for storage as baseline. If symptoms suggestive of viral infection develop then a sample will be taken and analysed with the baseline sample (See Section 6.3).
 See Pharmacokinetic time and events table for dose specific timepoints.
 Additional blood samples may be taken during the study if subject develops infection in order to measure LAG-3+ cells or other parameters as may be clinically or immunologically
- Pharmacogenetics sample can be taken any time after consent is signed.
 To calculate the correct dose, weight must be measured on Day -1 or Day 1 pre-dose.
 Triplicate. Only required if screening ECG not within 35 days of Day 1.
 Cohort 0.0015mg/kg last out patient visit will be on Day 29.
 Cohort 0.0075mg/kg last out patient visit will be on Day 57.

14.1.2. Healthy volunteers (DTH subjects)

Protocol Activity		st lenge					In C	linic Per	iod								Out P	atient	Visits	,			
			Day 28			Day	29 (Day 1	1)		Day 30 (Day 2 post- dose)	Day 31 (Day 3 post- dose)	Day 32 (Day 4 post- dose)											
	Day 1	Day 3	Day 28	Pre- dose	0 hour	2 hour post- infusion start	4 hour post- infusion start	post-	12 hour post- infusion start	post-	hours	72 hour post- infusion start	(Day 8 post-		15 post-	18 post-	22 post-	25 post-	29 post-	43 post-	Day 85 (Day 57 post- dose)	85 post-	
Window			±3d										±1d	±1d	±1d	±1d	±1d	±1d	±1d	±2d	±2d	±2d	±3d
Admission to the unit			Х																				
Discharge from the unit												X											
Brief Physical	Х		Х																				
Urine Drug and Alcohol Screen	Χ																						
Administer IV Dose (2 hour infusion)					4	n																	
Safety Assessme	nts																						
Vital Signs	Χ	X		Χ		X	X	X	X	X	X	X	X		Х		Χ		X	X	X	Χ	X
12 - Lead ECG	Χa			Х	⋖	b		Х				X											
Concomitant Medications	∢																						
Adverse Events Assessment / SAE'sc	4																						

Protocol Activity		st lenge					In C	linic Per	iod								Out P	atient	Visits	,			
			Day 28			Day	29 (Day 1	1)		Day 30 (Day 2 post- dose)		Day 32 (Day 4 post- dose)											
	Day 1	Day 3	Day 28		0 hour	2 hour post- infusion start	4 hour post- infusion start	post-	12 hour post- infusion start	post-	48 hours post- infusion start	72 hour post- infusion start	8 post-	11 post-	15 post-					43 post-	Day 85 (Day 57 post- dose)		149 (Day 121 post-
Window			±3d										±1d	±1d	±1d	±1d	±1d	±1d	±1d	±2d	±2d	±2d	±3d
Efficacy Assessn	nents	•		•	•								•	•			_		•	_			•
Visual Arm Inspection	Χα									Χe													
ID PPD Challenge	Χ ^f									Хf													
Bleb/ILH Assessment	Χe									Χe													
Ball Point Pen Technique		Х										Х	х		Х		Х						
Skin Biopsy		Χg										Χg											

	_																						
Protocol Activity		st lenge					In C	linic Per	iod								Out F	atient	Visits	•			
			Day 28			Day	29 (Day 1	1)		Day 30 (Day 2 post- dose)	Day 31 (Day 3 post- dose)	Day 32 (Day 4 post- dose)											
	Day 1	Day 3	Day 28	Pre- dose	0 hour	2 hour post- infusion start	4 hour post- infusion start	post-	12 hour post- infusion start	post-	48 hours post- infusion start	start	(Day 8 post-								Day 85 (Day 57 post- dose)		
Window			±3d										±1d	±1d	±1d	±1d	±1d	±1d	±1d	±2d	±2d	±2d	±3d
Laboratory Asses	ssmei	nts																					
Haematology	Χh		X					X	X			X	X	Х	Χ	Х	X	Х	X	Χ	Х	Х	X
Chemistry	Χh		Х					Χi	Χi			X	Х		Х		Χ		Χ	Х	Χ	Χ	Χ
Urinalysis	Χħ		Χ					X	Х			X	Χ		Χ		Х		Х	Χ	Х	Х	Х
CMV and EBV serology sample			х																				
Viral load sample (CMV, EBV, HSV, VZV)i			х																				
Immunogenicity Sample				X									Х						Х			Х	
PK Sample ^k					◀																		
Immune Cell Phenotyping				Х				Х		Х		Χ	Χ		Χ				Х		X	Χ	X
CD16 and LAG-3 Receptor occupancy				х				Х		Х		Х	Х		Х				Х		Х	Х	Х
Cytokine Sample				X				X	X	X	X												
G-CSF Sample				Χ				X		X		Χ	Χ		Χ				Χ	Χ	Х	Χ	Χ

Protocol Activity	1 Chal	st lenge					In C	linic Per	iod							Out P	atient	Visits	,			
			Day 28			Day	29 (Day 1	1)		Day 30 (Day 2 post- dose)	Day 31 (Day 3 post- dose)	Day 32 (Day 4 post- dose)										
	Day 1	Day 3	Day 28	Pre- dose	0 hour	2 hour post- infusion start	4 hour post- infusion start	post-	post-	24 hour post- infusion start	48 hours post- infusion start	72 hour post- infusion start	(Day 8 post-		15 post-	22 post-		29 post-		Day 85 (Day 57 post- dose)		
Window			±3d										_	±1d	_	_	_	_		±2d		±3d
sLAG-3 Sample				Χ				X		Х		Х	Χ		Χ			Χ	Χ	X	Χ	Χ
Blood Transcriptomics Sample				X						Х												
Ex vivo antigen/cytokine stimulation				х						Х												
In vitro LAG-3+ activity				X		Х							X									
PGx Sample	Χm																					

- Triplicate. Only required if screening ECG not within 35 days of Day 1.
 Continuous 2-lead ECG during infusion. Only significant abnormalities during this time will be databased.
- A targeted physical examination may take place if guided by AE reporting relating to Section 6.3.4, Section 6.3.5 and Section 6.3.6.
- d. Must be performed before ID PPD Challenge
- Bleb is assessed 5 minutes after ID injection and the immediate local hypersensitivity assessment 15-30 minutes after ID injection. See Section 5.10.1 for details.
- g. Only biopsy from one of the PPD sites preferably from the subjects non-dominant arm.
- h. If safety labs have been taken ≤7 days prior to challenge then these safety labs are not required. These samples can be taken on Day 1 or Day -1.
- Liver Chemistry and CRP only
- Viral load sample for storage as baseline. If symptoms suggestive of viral infection develop then a sample will be taken and analysed with the baseline sample (See Section
- 6.3).
 See Pharmacokinetic time and events table for dose specific timepoints.
 Additional blood samples may be taken during the study if subject develops infection in order to measure LAG-3+ cells or other parameters as may be clinically or
- m. Pharmacogenetics sample can be taken any time after consent is signed.
- To calculate the correct dose, weight must be measured on Day 28 or Day 29 pre-dose.

